Implementation of a Trimodal Prehabilitation Program as a Preoperative Optimization Strategy in Cardiac Surgery and Heart Transplant

NCT03466606

STUDY PROTOCOL AND STATISTICAL ANALYSIS PLAN.

Document upload date: August 27, 2024.

STUDY PROTOCOL AND STATISTICAL ANALYSIS PLAN:

Subproject: #1

A single-center, ambispective cohort study is designed involving consecutive elective heart transplantation candidates from July 2017 to July 2021 once officially included in the waiting list. The trial has obtained local ethical committee approval (HCB/2017/0708). Written consent will be obtained for all patients participating in the prehabilitation group.

- *Participants*

From July 2017, all patients included in the waiting list for elective heart transplantation will be considered for inclusion in the prehabilitation program. Exclusion criteria are clinical instability precluding exercise training, refusal, or unavailability to participate. Exercise training sessions will be delivered at the outpatient clinic and patients' agreement to attend twice weekly for at least eight weeks (intensive phase) is considered a mandatory requirement.

The control group will be consisted of a historical cohort of consecutive elective heart transplantation recipients from 2014 to 2017 (prior to the implementation of the prehabilitation program on July 2017), and contemporaneous elective heart transplantation recipients who will not be involved in the prehabilitation program due to logistic issues (waiting-list period <2 weeks or not being able to attend twice a week). Data from those patients will be obtained from the transplant database and hospital medical records.

- *Intervention*

A baseline assessment of prehabilitation patients will be performed during the first week after being included in the heart transplantation waiting list and all participants will be reassessed eight weeks thereafter, once the intensive training phase is completed.

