All patients will be invited to attend a weekly mindfulness group session. This anxiety-coping intervention is strongly recommended to those patients showing signs of

anxiety/depression (defined by a HADS score >8). A weekly 60-min group session of breathing and relaxation exercises will be conducted by a mindfulness-based stress reduction expert psychologist.

Usual care for both groups consists of regular cardiological follow-up with medical and heart failure nurse visits, physical activity recommendations, intravenous iron administration if iron deficiency anemia, and nutritional intervention if needed.

- *Costs*

The analysis will include heart transplantation surgical procedures, direct hospitalization (until discharge), and prehabilitation costs. Data will be obtained through microcosting techniques according to resource use, combined with diagnostic-related center-specific hospital fees. Prehabilitation costs include specialists' fees (physical therapist, nutritionist, and psychologist), gym structural costs (hospital-specific fee), and protein costs.

- *Outcomes*

Predefined main study outcome variables assessment will be blinded to the interventional groups and included: in-hospital complications according to Clavien-Dindo Classification and Comprehensive Complication Index (CCI), postoperative mechanical ventilation time, intensive care unit (ICU) length-of-stay and total hospitalization stay, destination at hospital discharge (home vs. rehabilitation facility), and hospital readmissions during the first 30 days as well as mortality at 30 days, 3 months, and 1 year. To minimize variability, it is important to note that decisions about ventilation time, ICU length of stay, and total length of stay as well as the discharge from ICU to a normal ward, and the destination at hospital discharge will follow standardized procedures according to the center protocol.

- *Statistical Analysis and Sample Size Estimation*

Study data will be exhaustively collected and managed using Research Electronic Data Capture (REDCap) tools.

Considering CCI as the primary outcome and assuming a pooled standard deviation of 20 units, the study would require at least a sample size of 28 for each group to achieve a power of 80% and a level of significance of 5% (two-sided), for detecting a true difference in means between the test and the reference group of -15 (from 50 to 35) units.

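### Subproject #1 draws prehabilitation patients at listing but controls from elective recipients, partly by a realised wait under 2 weeks, so the groups can differ in waiting time and urgency by definition

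*Combined protocol and SAP*

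**What the plan says.** All entry rules are in Subproject #1, Participants and the paragraph before it.

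- **Cohort.** The study is described as covering "consecutive elective heart transplantation candidates from July 2017 to July 2021 once officially included in the waiting list".
- **Prehabilitation group.** From July 2017, "all patients included in the waiting list for elective heart transplantation will be considered for inclusion in the prehabilitation program". The limits are: "Exclusion criteria are clinical instability precluding exercise training, refusal, or unavailability to participate". In addition, "agreement to attend twice weekly for at least eight weeks (intensive phase) is considered a mandatory requirement". Under Intervention, "A baseline assessment of prehabilitation patients will be performed during the first week after being included in the heart transplantation waiting list".
- **Historical controls.** These are "a historical cohort of consecutive elective heart transplantation recipients from 2014 to 2017", with no condition on waiting time.
- **Contemporaneous controls.** These are "contemporaneous elective heart transplantation recipients who will not be involved in the prehabilitation program due to logistic issues (waiting-list period <2 weeks"; the sentence then adds a second route, inability to attend twice a week.
- **Costs.** "The analysis will include heart transplantation surgical procedures, direct hospitalization (until discharge), and prehabilitation costs". The difference is control minus prehabilitation, with positive values read as savings.
- **Analysis.** The Statistical Analysis section plans t-tests or Mann-Whitney tests, chi-square or Fisher tests, quantile regression with no covariates named, and a bootstrap for costs. It gives no matching, restriction or adjustment on waiting time or urgency. It does not say how programme starters who die, are delisted, become urgent or are transplanted early are counted. Mortality at 30 days, 3 months and 1 year has no stated time origin.

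**The concern.** The groups are identified at different moments. A prehabilitation patient is identified soon after listing, before anyone knows how long the wait will be or whether the transplant will be elective. A control is identified at transplant, when both are known, and for contemporaneous controls a short wait is itself a reason to be one.

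If waiting time or urgency at transplant is related to postoperative complications, part of any CCI difference reflects the entry rules and not the programme. Costs are exposed too: programme spending begins on the waiting list, so an analysis limited to recipients would omit what was spent on starters who never reached transplant.

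**Working it through.** **1. The plan's own figure.** Inputs from the sample size paragraph: difference 15, SD 20, two-sided 5%, power 80%.

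n = 2 × (1.960 + 0.842)² × 20² / 15² = 27.9, so 28 per group, as stated. (The noncentral t gives 29, and 78.7% power at 28.) The figure reproduces and is not in dispute. It gives a scale: the standard error of the difference is 20 × √(2/28) = 5.35 CCI units.

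**2. The three sources side by side.**

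| Source | Identified at | Must have been transplanted | Wait condition | Elective status refers to |
|---|---|---|---|---|
| Prehabilitation | Listing | Not stated | None; agreement to attend only | Waiting list |
| Historical control | Transplant | Yes | None | Recipient |
| Contemporaneous control | Transplant | Yes | Wait under 2 weeks, or unable to attend | Recipient |

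Two differences follow from the definitions alone: the wait condition, and the moment to which elective status refers.

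**3. Waiting time (assumed inputs).** Let f be the excess share of short-wait patients among all controls over the prehabilitation group, and D their difference in mean CCI from longer-wait recipients. The shift is f × D.

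- f = 0.20, D = 10: 2 units, which is 2/15 = 13% of the planned effect.
- f = 0.10, D = 5: 0.5 units.
- f = 0.25, D = 10: 2.5 units.
- f = 0.50, D = 15: 7.5 units.

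The sign is that of D, which the documents do not give.

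**4. Urgency (assumed inputs).** If 10% of the prehabilitation group is transplanted urgently with mean CCI 20 units higher, and no such patient can be a control, the prehabilitation mean rises by 0.10 × 20 = 2 units, against the programme. Taken with the 2-unit case in step 3, the net distortion is 2 − 2 = 0 if short-wait patients do worse, or 2 + 2 = 4 units against the programme if they do better.

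**5. What a shift does to the test.** With 28 per group, SD 20, a two-sided 5% t-test and no true effect:

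| Net shift (CCI units) | False-positive rate |
|---|---|
| 0 | 5.0% |
| 2.5 | 7.5% |
| 5 | 15.1% |
| 7.5 | 28.1% |
| 10 | 45.1% |

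These rates hold for a selection difference from any cause; they do not estimate this one.

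**6. Programme cost (assumed inputs).** If a share p of starters is never transplanted and cost per starter is equal, programme cost per transplanted patient is 1/(1 − p) times the recipients-only figure: 1/0.95 = 1.05 at 5%, 1/0.85 = 1.18 at 15%, 1/0.75 = 1.33 at 25%.

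**The case against.** Several stronger readings are tempting, and the text does not support them.

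- *A patient enrolled on day 4 and transplanted on day 10 becomes a control, so patients move between groups.* Contemporaneous controls are recipients not involved in the programme. An enrolled patient is involved. The short wait is a reason for non-involvement, not a rule for reclassifying anyone.
- *Short waits are excluded from prehabilitation by rule.* They are not. The exclusions are instability, refusal and unavailability, and the eight-week condition is agreement to attend, not a wait that must be completed.
- *Deaths and delistings on the waiting list bias the CCI comparison.* Postoperative CCI exists only for recipients, so for that outcome both groups are already conditioned on transplant. These exits matter for the mortality time origin and for costs.

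It can also be said that the sentence about candidates describes the whole cohort, that a short wait is only one of two routes into one of two control sources, and that the plan never says when elective status is judged. All this is fair. But the prehabilitation group is still drawn from the list and assessed in the first week, and both control sources are still recipients.

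Finally, every magnitude above is assumed, and a 2-unit shift is only 2/5.35 = 0.37 standard errors. That also stands. So does the point that restricting or adjusting on waiting time and urgency among recipients could remove much of the problem; the plan provides for neither.

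**Conclusion.** The concern holds in a limited form. Following the stated rules directs short waits into the contemporaneous controls, leaves historical controls with no wait condition, and allows urgent transplants in the prehabilitation group but not among the controls. The last part rests on reading elective recipient as elective at transplant. The unadjusted tests do not deal with any of this.

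The documents fix neither the size nor the direction of the bias. The assumed inputs give shifts from 0.5 to 7.5 CCI units for waiting time, and the waiting-time and urgency effects may cancel or add. The cost omission arises only if the analysis is confined to recipients, which the plan does not state; it would then favour the programme.

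This should be corrected because it touches the primary outcome and costs, leaves mortality without a defined starting point, and is cheap to repair. It does not show that the comparison is invalid, and it implies no new sample size.

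**What to change.** 1. Judge elective status at listing for all three sources, taking listing date and status from the transplant database.
2. Make the main CCI comparison among recipients who waited at least 2 weeks in all three sources, using the plan's own cut-off. Report all recipients as a sensitivity analysis, keeping early-transplanted starters in the prehabilitation group.
3. Tabulate death, delisting and urgent transplant after listing by group, and state the time origin for mortality.
4. Charge the programme costs of starters who were never transplanted to the prehabilitation group.

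The cost is a change of definitions and a database query for listing date, status and reason for leaving the list; no new patients or assessments are needed. Short-wait controls and any early-transplanted starters drop out of the main comparison, so the short-wait route then supplies no one to it, and the 28 per group should be counted in the restricted set. The restriction sets a common minimum wait; it does not make longer waits equal, so the waiting-time distribution should be shown by source.

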Continuous variables will be described by mean (standard deviation) or median (interquartile range (Q1–Q3)) as appropriate, while categorical variables will be presented as frequencies (percentages). Costs will be described by median (interquartile range (IQR)), and the difference between control and intervention (prehabilitation) groups, so positive values should be interpreted as savings.

The normality of distribution will be assessed with the Shapiro-Wilk Test. Between-group comparison of continuous variables and costs will be performed using either Student's *t*-test or the Mann-Whitney U test according to their distribution while Pearson's χ^2 test or Fischer's test will be used for categorical variables. Quantile regression will be used for medians. To control for the usually skewed distribution of costs, a bootstrapping analysis will be performed to increase the robustness of the analysis.

All comparisons will be two-sided, with a significance level of 0.05. All statistical analyses will be made with R version 4.0.2, (R-Foundation, Vienna, Austria) software or STATA v.17 software.

Subproject: #2

This is a prospective, randomised, open-label, controlled trial with allocation ratio 1:1 comparing standard of care versus 4–6 weeks of a multimodal prehabilitation programme. The recruitment period is scheduled from March 2018 to January 2021. Both primary endpoint and baseline data will be blindly assessed. Intention-to-treat criteria will be used in order to define the analysis population; all randomised patients will be included in the analysis according to assigned group. The study protocol and informed consent have been evaluated and accepted by the Medical Research Ethics Committee at Hospital Clinic de Barcelona (2017/0708). The trial will be conducted according to the rules of Good Clinical Practice.

METHODS AND ANALYSIS

- Setting

This trial will be conducted in a single academic tertiary hospital in Barcelona, Spain (Hospital Clinic de Barcelona). Assessments and study interventions will be performed at the outpatient ambulatory infrastructure of Hospital Clinic de Barcelona. Surgery and postoperative hospitalization will take place in the aforementioned hospital.

-Eligibility criteria

Inclusion criteria: Patients older than 18 years old scheduled for CABG and/ or valve surgery, with an expected waiting time before surgery of 6 weeks or more and that accept to participate in this clinical trial.

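### Subproject #1 compares differently selected, non-randomised groups with no confounding control stated, so the primary CCI difference can partly reflect case-mix, waiting time or era

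*Combined protocol and SAP*

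**What the plan says.** The opening of Subproject #1 describes a single-centre ambispective cohort "involving consecutive elective heart transplantation candidates from July 2017 to July 2021 once officially included in the waiting list". The Participants section then builds the two groups by different rules.

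- **Prehabilitation group.** "Exclusion criteria are clinical instability precluding exercise training, refusal, or unavailability to participate". In addition, patients' "agreement to attend twice weekly for at least eight weeks (intensive phase) is considered a mandatory requirement".
- **Historical controls.** "The control group will be consisted of a historical cohort of consecutive elective heart transplantation recipients from 2014 to 2017", the period before the programme began in July 2017. No stability, willingness or attendance filter is stated for them.
- **Contemporaneous controls.** These are "contemporaneous elective heart transplantation recipients who will not be involved in the prehabilitation program", for logistic reasons only: a wait under two weeks, or inability to attend twice a week.

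The split between the two control sources is not given. For controls, "Data from those patients will be obtained from the transplant database and hospital medical records". The Intervention section describes the baseline assessment for prehabilitation patients only.

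Under Statistical Analysis and Sample Size Estimation, CCI is the primary outcome and the target is 28 patients per group. The planned comparison reads "Between-group comparison of continuous variables and costs will be performed using either" a t-test or a Mann-Whitney U test, depending on the distribution. Categorical variables get a chi-square or Fisher test. Quantile regression is named for medians, without covariates. A bootstrap is added because costs are skewed.

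**The concern.** Without randomisation, a crude two-sample test estimates the programme effect only if the groups are otherwise exchangeable. Here they differ by construction in three ways:

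- era (historical controls against patients from July 2017);
- waiting time (some contemporaneous controls are controls because they waited under two weeks);
- ability and willingness to attend and, against the historical controls, stability.

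None of the planned methods addresses this. Quantile regression could carry covariates, but none is named. The bootstrap deals with the shape of the cost distribution. The document does contain a rule for imbalance (absolute standardised difference above 0.10, then adjust), but it sits in the perioperative neurocognitive disorders subproject, which belongs to the randomised Subproject #2. A rule is thus written where randomisation already protects and none where it does not.

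At stake are the subproject's primary comparison and, with it, the comparisons of stay and cost. A larger sample would not remove the bias.

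**Working it through.** **Inputs from the plan** (Subproject #1, sample size paragraph): target difference 15 CCI units (50 to 35), SD 20, two-sided 5%, power 80%, 28 per group.

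**Step 1: the plan's own figure.** n = 2 × [20 × (1.960 + 0.842) / 15]² = 27.91, rounded up to 28. Power at 28 is 80.1% by the normal formula and 78.7% by the noncentral t. The stated sample size reproduces. The arithmetic is sound, but it assumes exchangeable groups.

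**Step 2: what an assumed bias does to the crude test.** SE = 20 × √(2/28) = 5.345. With 54 degrees of freedom the critical t is 2.005, so the smallest significant difference is 2.005 × 5.345 = 10.72 units. If confounding shifts mean CCI by b units, the test statistic is noncentral t with parameter b/5.345. The values of b are assumptions, since the documents give none.

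| b (units) | b as share of 15 | No true effect, b towards prehabilitation: significant in its favour | Same, two-sided total | True effect 15, b against prehabilitation: power |
|---|---|---|---|---|
| 0 | 0% | 2.5% | 5.0% | 78.7% |
| 1 | 7% | 3.8% | 5.4% | 73.0% |
| 2 | 13% | 5.6% | 6.6% | 66.6% |
| 4 | 27% | 11.0% | 11.4% | 52.4% |
| 5 | 33% | 14.9% | 15.1% | 45.1% |

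For scale, a risk factor 20 percentage points more common in one group and worth 20 CCI units gives b = 0.20 × 20 = 4. This too is an assumption.

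**Step 3: what adjustment does to power at 28 per group.** Let R²y be the share of CCI variance that the covariates explain, and R²x the share of group membership that they explain. The required size becomes 27.91 × (1 − R²y)/(1 − R²x). It stays at 28 only if R²y is at least R²x. All covariate values below are assumed.

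- *One of four covariates imbalanced.* With a standardised mean difference (SMD) of 0.5–0.8 and R²y of 0.15–0.20, simulation of a linear regression with HC2 standard errors gives power of about 75–81%. Without a true effect, the chance of a significant favourable result is about 2.6–2.9%. For comparison, SMD 0.5 with R²y 0.15 implies a crude bias of 0.5 × √0.15 × 20 = 3.9 units.
- *All four imbalanced and independent.* In equal groups R²x = (4 × SMD²/4)/(1 + 4 × SMD²/4), which is 0.25/1.25 = 0.20 at SMD 0.5 and 0.64/1.64 = 0.39 at SMD 0.8. The residual SE is 5.345 × √[(1 − R²y)/(1 − R²x)], with 56 − 2 − 4 = 50 degrees of freedom:

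| R²y | Power, SMD 0.5 | Power, SMD 0.8 |
|---|---|---|
| 0.05 | 71% | 60% |
| 0.15 | 76% | 64% |
| 0.20 | 79% | 67% |

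**The case against.** The plan has real safeguards. Both groups are limited to elective transplantation. Usual care is described as common to both. Outcome assessment is blinded, and decisions on ventilation, stay and discharge follow centre procedures. These reduce variability in measurement and care, but they do not make the patients alike at baseline.

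Four stronger readings are tempting, and the documents do not support them.

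- *Unstable or refusing programme-era patients become controls.* They do not. Contemporaneous controls are restricted to logistic reasons, so the missing stability filter concerns the historical controls only.
- *No baseline comparison is planned.* The general wording on describing and comparing variables is not confined to outcomes, so a crude baseline table is compatible with it. What is absent is standardised differences and any action on imbalance.
- *The plan makes a causal cost claim.* The statement that positive values mean savings mainly fixes the sign of control minus prehabilitation; Subproject #2 uses the same convention.
- *The result is biased in favour of prehabilitation.* A stability filter would tend that way against historical controls, but waits under two weeks could act in either direction.

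It can also be said that the illustrated biases are assumed, that 1 unit matters little, and that none of them reaches the 10.7-unit threshold without help from chance. All of that stands. The case therefore rests on how the groups are formed, not on any particular figure.

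**Conclusion.** The concern holds as a gap in the plan: a non-randomised primary comparison between groups selected by different rules, with no prespecified handling of confounding. Followed as written, the CCI, stay and cost differences can partly reflect case-mix, waiting time or era.

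Size and direction are unknown. Under the assumed biases of 2 to 5 units towards prehabilitation, the chance of a falsely favourable result rises from 2.5% to between 5.6% and 14.9%. Biases of the same size in the other direction would cut power for a true 15-unit benefit from 78.7% to between 66.6% and 45.1%. These figures rest on 28 per group, SD 20 and a t-test. They show sensitivity and do not estimate the actual bias. The sample size calculation itself is not at fault.

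**What to change.** 1. Make the primary CCI comparison a prespecified covariate-adjusted regression with small-sample robust standard errors (HC2, for example). Use a short list of about 3–5 prognostic factors, first confirmed as recorded for both groups in the transplant database or medical records. Keep the crude test as secondary.
2. Report baseline standardised differences by group and by control source.
3. Where the data allow, add sensitivity analyses: a common waiting-time landmark, the instability exclusion applied to historical controls, and historical and contemporaneous controls analysed separately. A two-week landmark does not resolve patients transplanted between weeks 2 and 8, and this should be stated.
4. Describe CCI and cost differences as associations with residual confounding, and keep savings as a sign convention only. The document was uploaded in August 2024. If outcomes have already been analysed, label the adjusted analysis post hoc.

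**Cost.** The analysis and chart-review work is modest, though older charts may not record instability precluding exercise. Precision may fall. Against the planned 80%, adjusted power at 28 per group is about 75–81% if one of four covariates is imbalanced and about 60–79% if all four are. About 80% is kept only if the covariates explain at least as much of CCI as of group membership. Sensitivity analyses that drop controls lose more: with 20–22 controls left, unadjusted power is 71–73%. Adjustment removes only confounding by factors measured in both groups.
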